2.2.2 Depression, depression treatment, and CVD risk in the general population

Thirty years of evidence indicates that depression is an independent risk factor for CVD (26). Meta-analyses have shown that adults with depressive disorders or elevated symptoms have a 64% greater risk of future CVD (27, 28). The depression-CVD relationship is comparable in strength to conventional CVD risk factors and is independent of other emotional factors (29). In addition, CVD risk increases with depression severity (27). Finally, depression has been linked to several atherogenic factors (30, 31), which supports the biological plausibility of the depression-to-future-CVD connection. Because depression meets 8 of Hill’s 9 criteria for causation (32), it is reasonable to conclude that depression is an independent, and potentially causal, CVD risk factor. The criterion not yet met is experimental evidence; however, our recently published study (33) indicates that depression treatment may be a CVD primary prevention strategy.

To date, few clinical trials have evaluated if depression treatments reduce the likelihood of CVD events (34-38). In general, these trials have not observed the anticipated benefits. A key study was the Enhancing Recovery in Coronary Heart Disease (ENRICH) Patients trial, in which 2,481 post-MI patients with depression and/or low social support were randomized to cognitive behavioral treatment or usual care. After 29 months, no difference in nonfatal MI or death was found (34). Similar negative results were observed in the Myocardial Infarction and Depression Intervention Trial (MIND-IT), in which depressed post-MI patients were randomized to a staged pharmacologic intervention or usual care (38).

We recently proposed a novel explanation: the depression interventions in past trials, all of which involved patients with pre-existing CVD, may have been delivered too late in the natural history of CVD (39). We hypothesized that treating depression before, versus after, the onset of clinical CVD could reduce risk of CVD events because: (1) earlier treatment of another CVD risk factor, hypercholesterolemia, yields more pronounced benefits (40-43), (2) depression exerts a cardiotoxic influence early in CVD pathogenesis (22, 29, 44, 45), (3) depression treatments may have greater antidepressive efficacy prior to clinical CVD onset (46-48), and (4) conventional prognostic factors may override depression's effect during the later stages of CVD (15, 49). To evaluate our hypothesis, we conducted an 8-year follow-up study (33) of the Improving Mood-Promoting Access to Collaborative Treatment (IMPACT) trial (48), in which older depressed patients were randomized to a collaborative stepped care intervention involving antidepressants and psychotherapy or usual care. Results supported our hypothesis. IMPACT patients (24/85=28%) without baseline CVD had a 48% lower risk of first MI or stroke (HR=0.52, 95% CI: 0.31-0.86) than Usual Care patients (39/83=47%). There was no treatment benefit among patients with baseline CVD. These findings strengthen the case for depression being a causal CVD risk factor and suggest that depression treatment is a potential CVD primary prevention strategy.

2.2.3 Associations between depression and depression therapy with inflammation, coagulation, and endothelial function in the general population

Systemic inflammation is one candidate mechanism that might explain how depression promotes CVD (50). A recent meta-analysis revealed that inflammatory markers, including IL-6 and hsCRP, are upregulated in depressed individuals (51). Depression also predicts increases in inflammatory marker levels up to 10 years later (51-53). Notably, the inflammatory markers elevated in depression are predictive of incident CVD (46). Depression-related dysfunction in the hypothalamic-pituitary-adrenal (HPA) axis and the autonomic nervous system, two systems that normally exert anti-inflammatory effects, have been proposed to explain how depression may promote inflammation (50, 53). Selective serotonin reuptake inhibitors (SSRIs) have been found to reduce IL-6 levels in depressed patients (54, 55), and this potentially beneficial effect seems limited to those whose depression improved (56-60). In addition, two small trials in patients with cancer or recent CABG found that cognitive behavioral treatment led to reduced IL-6 and hsCRP levels (61, 62), results similar to our preliminary data (section c6).

Depression has been variably associated with altered coagulation (18, 19, 31, 63-71). For instance, Lukas et al. (18) found that depressive disorders were associated with higher D-dimer levels, and von Kanel et al. (72, 73) found that acute psychological stressors in depressed patients led to higher D-dimer levels even after the stressors resolved. However, other studies have not observed similar associations (70, 74, 75). Little is known about the effects of depression treatment on altered coagulation, although a small study recently found that SSRI treatment may counteract elevated D-dimer levels associated with depression (64). Given the known utility of D-dimer in predicting HIV-CVD and the availability of this marker in the large VACS Biomarker Cohort, it is reasonable to study this marker of coagulation in relation to depression in this application. Endothelial dysfunction is also a candidate mechanism through which depression may increase CVD risk. A recent meta-analysis of 12 studies revealed the depression is moderately and inversely associated with FMD in the general population (overall $r=0.19$, $p=0.001$) (22). Our pilot results (section c4) are in line with these findings. A few small studies have suggested improvements in FMD or nitric oxide availability with SSRI treatment (23, 76, 77). Of note, SSRIs could reduce inflammation, coagulation, and endothelial dysfunction either via depression reduction or potential direct medication effects on these systems (78-80). We are not aware of any studies, other than our pilot trial (section c6), that have examined the effect of cognitive behavioral treatment for depression on endothelial function.

2.2.4 HIV, depression, and CVD risk

Depression is highly prevalent in the HIV-infected population, including in those receiving ART, with rates ranging from 20-40% (81-84). Several studies have suggested that the rate of depression in HIV is two-fold greater than in uninfected individuals (85). Given this high prevalence of depression, it stands to reason that this comorbidity may appreciably contribute to HIV complication. In fact, chronic depressive symptoms are associated with greater Framingham risk scores in HIV-infected persons (86), but our recent work is the first to show a relationship between depressive disorders and HIV-CVD (section c1). This current application seeks to identify the underlying mechanisms for this association and a new intervention to mitigate the risk of depression-related CVD in HIV.

2.2.5 Endothelial progenitor cells, soluble markers of monocyte activation, and cardiovascular disease

Endothelial Progenitor cells (EPCs) are defined as cells that are found circulating within the bloodstream and when cultured are capable of taking on the phenotypic and functional characteristics of mature endothelial cells. EPCs are thought to home in to sites of vascular damage and assist in angiogenesis by either direct integration into the endothelium or via paracrine stimulatory mechanisms. Multiple studies have now shown an inverse relationship between metabolic syndrome, CAD, and levels of circulating EPCs (87).

The published literature regarding EPCs in HIV are conflicting with some showing no difference between HIV-infected and uninfected groups and others suggesting a lower level in those with HIV and an inverse association with FMD (88-92). These studies use differing methodologies in assessing EPCs. However, the laboratory of [name] and has established a 'gold standard' phenotype for differentiating EPCs from endothelial colony forming cell (ECFCs) (93). We will employ this method in the current study for assessing the relationships between depression treatment and ECFC levels.

In addition, CD14⁺CD16⁺ cell subsets and the soluble monocyte activation markers sCD14 and sCD163 have been linked to greater inflammatory atherosclerotic disease burden in those with HIV infection (94). Moreover, monocyte activation has been linked in some studies to more severe depression (95, 96). As such, these markers of monocyte activation will also be measured in this trial. Understanding the relationship between these cell subsets, monocyte activation, endothelial dysfunction in HIV during depression treatment is crucial to the continued efforts to explain the conferred increase in cardiovascular in those with HIV and possibly identify new biomarkers for risk assessment in this population.

2.2.6 Cognitive behavioral treatment to improve depression: the *Beating the Blues* program

Beating the Blues (U Squared Interactive; see www.beatingthebluesus.com for a video tutorial) is an empirically supported, stand-alone, cognitive behavioral treatment program appropriate for adults with little computer experience and at least a 5th-6th grade reading level (97). This program utilizes an interactive, multimedia format to deliver eight 50-minute, weekly sessions, the structure and content of which mirror face-to-face cognitive behavioral treatment. Although sessions are tailored to each patient's problems, general topics include challenging dysfunctional thoughts, activity scheduling, problem solving, graded exposure, task breakdown, sleep management, and relapse prevention. Patients are also assigned tailored homeworks. *Beating the Blues* is an appropriate selection for the proposed trial, as it is efficacious, acceptable, and an excellent fit with our goals. First, it has more empirical support than any other computerized psychotherapy, including a positive randomized trial of 274 depressed patients (98, 99). It is a potent intervention (98-106), with effect sizes comparable to face-to-face cognitive behavioral treatment (107). In our pilot trial, we also observed a large *Beating the Blues* effect size for depressive symptoms ($d=1.33$). Because of its strong evidence base, the National Institute for Health and Care Evidence recommended this program for managing depression in the English National Health Service in 2006 (108). In addition, since 2012, *Beating the Blues* has been listed in the Substance Abuse and Mental Health Services Administration's (SAMHSA) National Registry of

Evidence-based Programs and Practices. Second, *Beating the Blues* has been shown to be acceptable to patients (97, 105, 106, 109). Third, *Beating the Blues* is an excellent fit with our long-term goal of equipping HIV clinicians with a new tool to simultaneously manage depression and CVD risk in their patients, given that it is a safe, inexpensive, and easily implemented intervention due to the lack of dependence on trained therapists.

2.2.7 Flow-mediated dilation (FMD) of the brachial artery

Endothelial dysfunction is the impaired ability of the vascular lining to maintain normal homeostasis. Endothelial dysfunction is an early precursor to atherosclerosis and has been shown to predict future cardiovascular events in most population studies (110-112). Improvement in endothelial function, as measured by FMD of the brachial artery, is associated with a reduced risk of future cardiovascular events (113, 114). FMD is a non-invasive technique using high-resolution ultrasound which was developed to measure changes in brachial artery diameter due to a stimulus (115), with results correlating closely with coronary endothelial function (116, 117). Measurements are made before and after endothelium-dependent and endothelium-independent stimuli (118). The endothelium-dependent stimulus is hyperemic blood flow triggered after the release of an inflated blood pressure cuff around the forearm. The shear stress from the increased blood flow subsequently causes endogenous vasodilators, predominantly nitric oxide, to be released from the endothelium which then relaxes the vascular smooth muscle. This flow-mediated dilation (FMD) of the brachial artery is thus a measure of the endothelium's ability to respond normally to hyperemic shear stress. A second stimulus, nitroglycerin, which directly relaxes smooth muscle is then applied to determine the smooth muscle's functional capacity. This endothelium-independent measurement is called nitroglycerin-mediated dilation (NTGMD). If FMD is low, but NTGMD is normal, the endothelium, and not the smooth muscle, can be safely assumed to be dysfunctional. FMD and NTGMD are calculated as the percent increases, respectively, in diameter.

FMD is an ideal measure of cardiovascular risk in this current trial for several reasons. First, as a continuous measure, use of FMD as a CVD endpoint in the proposed trial provides greater statistical power and thus requires smaller sample sizes compared to a hard endpoint trial. Second, as opposed to anatomic measurements such as coronary calcium or carotid intima media thickness, FMD is a dynamic and mechanistic physiologic assessment of vascular function. Third, FMD responds within days to weeks of an intervention (119) and, thus, can be used to detect changes in cardiovascular risk quickly, which is vital when evaluating the potential efficacy of a new intervention such as cognitive behavioral treatment.

[figure not shown]
2.3 Preliminary Studies

2.3.1 Depression predicts incident CVD in HIV

We first sought to determine whether depressive disorders predict incident CVD in the HIV-infected population as they do in the general population. We previously found that HIV infection independently increases the risk of incident acute MI by 48% overall and by 39% in those with HIV-1 RNA levels <500 copies/ml in the VACS Virtual Cohort (120). Using this same cohort, we examined relationships between the presence of a depressive disorder at baseline and 6-year incidence of incident MI (CROI 2014). Of the 27,350 HIV-infected male veterans free of CVD at baseline (1998-2003), 6,219 (23%) had a baseline depressive disorder (ICD-9 codes 296.2, 296.3, or 300.4) and 367 (1.3%) suffered incident acute MI [defined using enzyme and EKG clinical data, inpatient ICD-9 code 410 in Medicare data, or ICD-10 code I21 as underlying cause of death on the death certificate] during the follow-up period (2003-2009). Cox models adjusted for demographic factors (age, race/ethnicity), CVD risk factors (hyperlipidemia, hypertension, smoking, diabetes, body mass index), and other potential confounders (hepatitis C infection, renal disease, alcohol and cocaine abuse, hemoglobin level, CD4 cell count, HIV-1 RNA level, antiretroviral medications) revealed that the presence of a baseline depressive disorder was an independent predictor of incident acute MI (HR=1.31, 95% CI: 1.03-1.67,

p=0.03). Our results (a) confirm that depressive disorders are highly prevalent in HIV-infected adults and (b) are the first to indicate that depression is a novel candidate risk factor for HIV-CVD events.

2.3.2 Depression treatment prevents first CVD events

[figure not shown]

Depression treatment has been unsuccessful in preventing subsequent CVD events in HIV-uninfected patients with pre-existing CVD. Providing depression treatment as primary prevention, however, appears to hold promise. As reported in our 2014 paper in *Psychosomatic Medicine* (33), we tested our hypothesis that treating depression before clinical CVD onset reduces the risk of CVD events by conducting an 8-year follow-up study of the Indiana sites participating in the IMPACT trial (48, 121). In that multisite RCT, 1801 depressed primary care patients aged ≥ 60 years were randomized to the IMPACT depression intervention (a collaborative stepped care intervention involving primarily SSRIs and/or brief cognitive behavioral treatment) or usual care. The 235 patients (76% female, 47% Black) from the Indiana sites were assessed for hard CVD events during follow-up using electronic medical record data linked with Medicare/Medicaid claims.

During follow-up, 119 patients (51%) had a hard CVD event (MI or stroke). As hypothesized, we detected a Treatment x Baseline CVD interaction ($p=0.021$), indicating that time to CVD event varied across the groups (Figure). Among the 168 *without baseline CVD*, IMPACT patients had a 48% lower risk of a hard CVD event than Usual Care patients (28% vs. 47%, HR=0.52, 95% CI: 0.31-0.86; $p=0.01$). Highlighting clinical significance, the number needed to treat to prevent one hard CVD event over 5 years was just 6.1. In contrast, among the 67 patients with baseline CVD, the likelihood of a CVD event did not differ between arms (86% vs. 81%, HR=1.19, 95% CI: 0.70-2.03; $p=0.52$), consistent with prior trials (34, 38). A similar pattern of results was found for men and women, for MI and stroke, and after adjustment for potential confounders. The IMPACT intervention was efficacious for depression treatment among patients without ($p<0.001$) but not with baseline CVD ($p=0.83$). In sum, we found that depression treatment, delivered before clinical CVD onset, halved the excess risk of first CVD events among depressed, HIV-uninfected adults, suggesting that depression treatment could be used as CVD primary prevention strategy.

2.3.3 Depression is associated with lower FMD

In a pilot study at Indiana University, we examined the cross-sectional relationship between depression and FMD in 35 HIV-uninfected primary care patients. Participants were 41-72 years old (66% female, 49% non-white) with no history of CVD or other chronic conditions. A total of 29% screened positive for depression defined as Patient Health Questionnaire-9 (PHQ-9) score ≥ 10 , which has 88% sensitivity and 88% specificity for major depressive disorder (122). Values [mean (SD)] for the PHQ-9 scores [6.0 (6.5)] and FMD [4.6% (3.1%)] fell within expected ranges. As is shown in the Figure, mean FMD of depressed adults was significantly lower than that of non-depressed adults (2.76% vs. 5.32%; $p = 0.045$), which is consistent with prior studies (22). Adjustment for brachial artery diameter, which is the strongest variable associated with FMD reactivity, increased the FMD difference to 3.5% (2.08% vs. 5.60%). This difference is likely clinically meaningful given that a 1.0% higher baseline FMD predicted a 6% lower risk of CVD events over five years in the Multi-Ethnic Study of Atherosclerosis (123, 124).

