3.6 Brachial artery reactivity indices

FMD and NTGMD will be measured according to established guidelines (126) at both Entry Visits, the Week 12 Visit, and the Week 24 Visit. These measurements will be performed at the ICRC.

Brachial reactivity measurements have considerable day-to-day variability. Variables that will transiently affect vasomotor function include environmental conditions, tobacco and alcohol use, diet, and medications (127). Therefore, it is desirable to control these factors in order to obtain results that more accurately reflect the underlying condition being studied. Therefore, the room temperature will be controlled at 68-71°F. The participant will rest supine for 10 minutes prior to imaging. Participants will be told to not use tobacco-containing products or eat or drink anything other than water for 8 hours prior to the study. Female participants will first have urine pregnancy testing performed prior to the ultrasound tests; if the participant is found to be pregnant, the participant's participation will end.

A 10 mHz linear array vascular probe for B-mode imaging will be used to visualize the brachial artery. Data will be stored on a compact disc for backup and also on the IU server with password protection. ECG leads will be placed on the participant's chest and automatic blood pressure cuff to left upper arm, set at q.15 minutes. A small forearm cuff is placed on the widest part of the participant's proximal right forearm

(approximately 1-2 cm distal to the antecubital fossa). The brachial artery will then be located with the image optimized for best resolution of all three layers of the anterior and posterior walls (with special emphasis on identifying the media-adventitia interface). Three consecutive cardiac cycles of B-mode images of the brachial artery to the disks will be acquired and stored.

After this baseline evaluation, the measurement of endothelium-dependent vasodilation, or FMD, due to increased blood flow will begin. The forearm pressure cuff will be inflated to 250 mmHg for 5 minutes. At that time, imaging will be switched to B-mode. At 60 and 90 seconds after cuff deflation, three consecutive cardiac cycles of B-mode images of the brachial artery to the disc will be acquired and stored. The greater of the two diameters measured at these time points will be used for FMD analysis.

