9.10 Analysis Plan for the Primary Objective

To test our primary hypothesis, an analysis of covariance (ANCOVA) will be performed to test for treatment group differences in Week 12 FMD adjusted for baseline FMD using the intent-to-treat set. Statistical significance will be considered if two-sided p-value <0.05. This analysis will be also repeated using the per-protocol set.

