9.11 Analysis Plan for Secondary Objectives

Both unadjusted comparisons and adjusted comparisons between UC and BtB will be performed for secondary outcomes defined in 1.2.1-1.2.3. For adjusted comparisons, multiple linear regression models will be constructed to include treatment group, baseline characteristics [demographics, SCL-20 scores, tobacco/exercise/adherence questionnaire results, ART drugs/regimens (including efavirenz (142-144)), antidepressant use, co-morbidities, CD4 cell counts, and HIV-1 RNA levels], and time-varying characteristics (changes in SCL-20 scores, questionnaire results, CD4 cell counts, ART drugs/regimens, HIV-1 RNA levels) to determine their effects on the outcomes. Pearson and Spearman correlation coefficients will be estimated for FMD, IL-6, hsCRP, D-dimer, circulating EPCs/ECFCs levels, and markers of monocyte activation (CD14+CD16+ cell proportions and sCD14/sCD163) with PHQ-9 and SCL-20 scores at baseline. These analyses will be performed for both the intent-to-treat set and the per-protocol set. Dose-response relationships between 12- and 24-week FMD and the number of BtB sessions, which have a range from 0 to 8, will be explored.

Safety assessments will be performed using the safety dataset. HIV-1 RNA levels and CD4 cell counts of the BtB arm during the trial will be summarized and compared to the UC arm.

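### The primary Week 12 FMD model omits pre-randomization brachial diameter, forgoing a possible small gain in precision and leaving chance imbalance in diameter unadjusted

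*Combined protocol and SAP*

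**What the plan says.** - **Endpoint.** Section 2.2.7: "FMD and NTGMD are calculated as the percent increases, respectively, in diameter". Resting diameter is therefore the denominator of the primary endpoint.
- **Importance of diameter.** Section 2.3.3, on 35 HIV-uninfected primary care patients compared by depression screening status: "Adjustment for brachial artery diameter, which is the strongest variable associated with FMD reactivity, increased the FMD difference to 3.5" (percentage points).
- **Availability.** Section 3.6 schedules scans "at both Entry Visits, the Week 12 Visit, and the Week 24 Visit". Each scan opens with resting images, and then: "After this baseline evaluation, the measurement of endothelium-dependent vasodilation, or FMD, due to increased blood flow will begin". Section 6.2.5.9 requires the brachial ultrasound measurements to go on the CRFs.
- **Primary model.** Section 9.10 plans an ANCOVA to "test for treatment group differences in Week 12 FMD adjusted for baseline FMD using the intent-to-treat set". It names no other covariate.
- **Secondary models.** Section 9.11: "For adjusted comparisons, multiple linear regression models will be constructed to include treatment group, baseline characteristics". The list that follows covers demographics, questionnaires, antiretroviral and antidepressant use, co-morbidities, CD4 count and HIV-1 RNA, but not diameter.

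The documents give no reason for leaving diameter out.

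**The concern.** The protocol ranks diameter above every other correlate of FMD and adjusted its own preliminary comparison for it. The randomized analysis then drops it, although the value has to be measured to compute FMD at all.

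Two separate things are at stake:

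- **Precision and chance imbalance.** If baseline diameter still predicts Week 12 FMD once baseline FMD is in the model, omitting it leaves removable variance in the treatment effect and leaves any chance difference in diameter between arms unadjusted.
- **Interpretation.** FMD% can move because the artery dilates more or because its resting diameter has changed. No planned analysis shows resting diameter or absolute dilation by arm, so a reader could not tell which happened.

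**Working it through.** **1. The plan's own sample size (section 9.3).** Inputs: difference 1.7 points, effect size 0.61, power 0.80, Type I error 0.05 (9.3), two-sided (9.10), 1:1 allocation (9.2), 20% attrition (9.3).

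- Implied SD = 1.7 / 0.61 = 2.79. The pilot trial in 2.3.5 gives √[(12 × 2.86² + 15 × 2.72²) / 27] = 2.78, so the two agree.
- Normal approximation: 2 × (1.96 + 0.84)² / 0.61² = 42.2, so 43 per arm.
- Noncentral t: power 0.798 at 43 per arm and 0.808 at 44 per arm, so 44 per arm, 88 in total.
- 88 / 0.80 = 110.

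The stated figures reproduce. The pilot effect behind them was adjusted for pre-treatment FMD only, so the sample size matches the planned ANCOVA and does not rely on diameter.

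**2. The preliminary shift (section 2.3.3).** Unadjusted: 5.32 − 2.76 = 2.56. Adjusted for diameter: 5.60 − 2.08 = 3.52. This compares depressed with non-depressed people, not randomized arms.

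**3. Precision if diameter is added.** Let δ be the share of residual variance, after baseline FMD, that baseline diameter explains. The documents do not give δ, so a range is assumed. The standard error is multiplied by √(1 − δ), and the equivalent gain in participants is 88 × δ / (1 − δ).

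| δ (assumed) | Fall in SE | Equivalent participants on 88 |
|---|---|---|
| 0.02 | 1 − √0.98 = 1.0% | 1.8 |
| 0.05 | 1 − √0.95 = 2.5% | 4.6 |
| 0.10 | 1 − √0.90 = 5.1% | 9.8 |

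**4. Power and chance imbalance.** Write r for the partial correlation of baseline diameter with Week 12 FMD given baseline FMD, so δ = r². Power uses 44 per arm, effect size 0.61 / √(1 − r²) and 84 degrees of freedom. The standard deviation of a chance difference in mean diameter is √(2/44) = 0.213 SD units. An imbalance of that size shifts the unadjusted effect by r × 2.79 × 0.213.

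| r (assumed) | Fall in SE | Power | Shift in FMD points |
|---|---|---|---|
| 0 | 0% | 0.807 | 0 |
| 0.1 | 0.5% | 0.811 | 0.06 |
| 0.2 | 2.0% | 0.823 | 0.12 |
| 0.3 | 4.6% | 0.843 | 0.18 |
| 0.5 | 13.4% | 0.904 | 0.30 |

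The r = 0.5 row lies well beyond the 2% to 10% range (δ = 0.25) and is shown only as an outer limit. The target difference is 1.7 points.

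**5. Numerator or denominator.** For illustration, take the pilot usual-care baseline FMD of 2.51% (2.3.5) and assume resting diameter falls by 1.6%.

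- Same dilation in millimetres: 0.0251 / 0.984 = 2.55%, a rise of 0.04 points.
- Same peak diameter: 1.0251 / 0.984 − 1 = 4.18%, a rise of 1.67 points, about the whole design target.

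Both cases have the same baseline diameter, so a baseline covariate cannot tell them apart. Follow-up diameter and absolute dilation by arm can.

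**The case against.** The planned model is valid and coherent. It follows the pilot randomized trial that supplied the effect size, it meets its 80% power without diameter, and section 3.3 already schedules two pre-randomization scans to steady the baseline. Section 2.3.3 shows a cross-sectional association only. It does not show that diameter predicts Week 12 FMD once baseline FMD is known, and baseline FMD already carries part of the effect. All of this stands. It limits the size of the point but gives no reason to leave the covariate out.

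Nitroglycerin-mediated dilation is measured at the same visits to separate endothelial from smooth-muscle response. But it too is a percent change in diameter, it appears nowhere in the analysis plan, and participants with migraine skip it (6.2.5.9).

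A reader might infer three stronger claims, none of which the documents support:

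- **That the treatment effect will be biased by roughly the preliminary shift, 2.56 to 3.52.** That comparison was not randomized, so diameter could differ systematically between its groups. Here randomization leaves only chance imbalance.
- **That the sample size is wrong.** It reproduces without any diameter adjustment.
- **That an FMD result could not be interpreted without the covariate.** The question of changing resting diameter is answered by reporting diameter and dilation by arm, not by a baseline covariate.

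**Conclusion.** The omission is real and cheap to repair, and its consequence is small. The intention-to-treat comparison is not systematically biased by it. Over an assumed 2% to 10% of extra residual variance explained, the standard error would fall by about 1% to 5%, worth about 2 to 10 participants on 88. Planned power of about 0.81 would rise to no more than about 0.85 (0.843 at r = 0.3, where δ = 0.09). If the extra share is near zero, nothing is gained and one degree of freedom is spent. A chance imbalance of one standard deviation would move the estimate by about 0.06 to 0.18 points for r between 0.1 and 0.3, against a target of 1.7.

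These sizes rest on the assumed partial correlation, on 44 evaluable participants per arm and on the SD of 2.79 implied by section 9.3. The point is worth acting on as a free improvement, not as the correction of an invalid analysis.

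**What to change.** In section 9.10, state that the Week 12 FMD ANCOVA includes treatment arm, baseline FMD and pre-randomization resting brachial diameter, the last taken as the mean of the two Entry Visit scans. Use the same diameter covariate for the Week 24 FMD comparison under 9.11. State also that the models will not adjust for diameter measured after randomization, because treatment may affect it.

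Separately, add two descriptive rows by arm at Weeks 12 and 24: resting diameter, and absolute dilation in millimetres. These let a reader see whether a change in FMD% comes from the numerator or the denominator.

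The cost is one degree of freedom, a short addition to the analysis plan and two table rows. No new measurement is needed, and the sample size does not change.
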